Random assignment to one of the two intervention groups at the hospital or health system level will be performed using matching^{45,46} and re-randomization⁴⁷ to ensure balance among several potential confounders: the volume of CT imaging performed, the setting type (integrated healthcare system vs. academic), KPSC vs. other institutions; racial and ethnic distribution; percentage of patients who are current, former, vs. never smokers; inclusion of patients with screening-detected nodules; frequency in using PET for patients with nodules 11-15mm; timing of notification letters to participants; and distribution of insurance type. A biostatistician at the Data Coordinating Center will generate the allocation scheme using statistical software developed in R by [name] at Vanderbilt^{45,46}. All participating organizations have agreed to accept random assignment to one of the two groups. While many of the participating

institutions operate more than one hospital, all but one will undergo randomization at the health system level, because their information systems for managing radiology results are centralized, so assigning individual hospitals to different groups would be difficult. The one exception is KPSC, which operates hospitals in 11 distinct medical service areas (MSA); clinical and administrative leaders at this site have agreed to randomization at the level of the MSA. Site PIs, clinical champions, and their multidisciplinary collaborators (including radiologists, primary care physicians, pulmonologists, oncologists and surgeons) will work with key administrative leaders and other clinicians to implement the assigned imaging protocols during the study period. Although randomization is at the hospital level, the unit of analysis will be the individual patient, and we will compare patients randomized to more vs. less frequent surveillance, after adjusting for potential clustering within sites.

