All CT scans performed for pulmonary nodule surveillance should be done using low radiation-dose technique, however, this vitally important aspect of imaging quality and safety is often overlooked during CT surveillance of lung nodules. Guidance on low radiation-dose techniques will be provided to each site and the study protocol will strongly recommend the use of these or equivalent low radiation-dose protocols for all follow up CT scans. During the first 3 months of the trial, site project coordinators will review the CT examinations and record radiation dose metrics (CT Volumetric Dose Index [CTDI vol] and Dose Length Product [DLP]) on a large sample of chest CTs performed at their site (10-50% depending on population; 100% for California hospitals as these data are included in the medical record by law) to determine if the

CTs were performed using appropriate techniques. Staff will be trained in radiation dose extraction techniques. Radiation dose metrics will be calculated monthly by site, provided to the Data Coordinating Center, and reviewed during regular meetings. Initiatives to ensure compliance with low-dose examinations will include site visits and radiology-specific lectures.

Table 4: Definition and Source Information for Outcomes, by Specific Aim				
Aim	At Risk	Outcome	Definition	Source
1	Participants with cancerous nodules	AJCC 7 th edition Stage >T1a or AJCC 8 th edition stage >T1b	Tumor size >20 mm at time of resection or radiotherapy.	Cancer Registry, EHR
		Time to diagnosis and treatment	Time to diagnosis and time to treatment with surgery, radiotherapy or chemotherapy, measured from date of index CT scan to date of first treatment.	
		Survival	Measured from date of index CT scan to death or censoring.	
2	All patients with nodules and access to email	Nodule-related distress	Measured with validated IES-R. Assessments performed 1-2 months after index CT scan, at 13-24 months, and at end of follow-up.	Self-administered web survey
		Anxiety	Measured with validated STAI-6. Assessments performed 1-2 months after index CT scan, at 13-24 months, and at end of follow-up.	
		General health status	Assessments performed 1-2 months after index CT scan, at 13-24 months, and at end of follow-up.	
		Satisfaction with evaluation	Measured with novel items, Likert-type scale. Assessment performed at 13-24 months and at the end of follow-up	

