We will measure effective radiation doses received by patients under the two different protocols. For the large subset of participants who received care in California, detailed information about CT technique must be documented in the radiology transcript by law. We estimate that approximately 22,000 individuals with nodules will be identified at one of the California sites during the 28-month enrollment period and we will randomly sample this group to obtain detailed information about diagnostic radiation exposure. We will also collect additional information about imaging protocols from radiologists at the sites outside of California who participate in the radiology Collaborative that we will set up as part of our quality assurance/quality improvement infrastructure.

We will collect data for three CT radiation dose metrics: the volume computed tomography dose index (CTDI_{vol}), the dose-length product (DLP), and the effective dose. CTDI_{vol} represents the average per-slice radiation dose, measured in milli-Gray (mGy), and reflects whether conventional or low dose settings are used for CT examinations. DLP is defined as the product of the CTDI_{vol} and the scan length, with units of mGy-cm, and reflects the total radiation output during the entire CT scan. With longer imaging times, the DLP will increase, or if a particular area is imaged multiple times, such as happens in multiphase studies, the dose length product from each scan is added together. CT scans done for the surveillance of nodules should use a shorter rather than a longer scan length. Both CTDI_{vol} and DLP are reported directly on the CT examination (typically stored as an image alongside the images from the CT scan) and can thus be extracted for any subjects through review of the images. Further, in California, by state law

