 - Pneumothorax requiring tube thoracostomy
 - Bleeding (pulmonary hemorrhage)
 - Acute respiratory failure
 - Acute renal failure
 - Allergic reaction to iodinated contrast material requiring hospitalization
 - Acute myocardial infarction
3. Cumulative radiation dose measured by DLP and effective dose

- Including radiation exposure from surveillance and diagnostic imaging following baseline CT scan through 2 years of follow-up (including 24 month exams).

Aim 4: Adherence with the recommended surveillance protocol

1. Radiologist adherence to assigned protocol
2. Physician adherence to ordering test
3. Patient adherence
 - a. Adherence to first recommended surveillance exam
 - b. Adherence to full protocol

Secondary endpoints:

Aim 1:

1. Proportion of lung cancers that are greater than 20mm, N0, MO
 - Measured as progression beyond AJCC 7th edition TNM stage of T1aN0M0 or AJCC 8th edition stage of T1bN0M)
2. Timeliness of lung cancer diagnosis
 - Measured as time from date of index CT scan to confirmed lung cancer diagnosis, defined as histologic confirmation via pathology, among individuals diagnosed with lung cancer.
3. Timeliness of lung cancer treatment
 - Measured as time from date of index CT scan to date of first treatment including surgery, radiotherapy or chemotherapy, among individuals diagnosed with lung cancer. If a patient receives no treatment, we will censor at end follow-up.
4. Overall survival of patients who prove to have a cancerous nodule,
 - Measured from date of index CT scan to death or censoring among individuals diagnosed with lung cancer.

Aim 2:

1. Patient general health status measured at 1-2 months, 13-24 months, and ≥ 25 months after nodule identification
2. Patient satisfaction with the evaluation process measured at 13-24 months and ≥ 25 months after nodule identification
3. Ordering specialist, primary care, and radiologist knowledge attitudes and beliefs about existing guidelines for pulmonary nodule evaluation measured at baseline
4. Provider satisfaction with the surveillance protocol and the evaluation process measured during the follow-up period

Aim 4: Adherence to use of low radiation-dose techniques

Hypotheses:

We specify the following hypotheses by aim:

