Descriptive statistics will be generated for radiation exposure and frequency of follow-up CT scans and other nodule-related resource utilization will be obtained by site and study arm. For each type of nodule-related resource utilization, we will also create a binary variable to indicate whether a patient has any exam of that type (1 yes and 0 no) and obtain the corresponding frequency. For H3a, to examine whether among all participants with a lung nodule ≤ 15 mm, more intensive surveillance will be associated with a greater number of specific follow-up tests and types of follow-up tests (e.g., imaging, non-surgical biopsy, surgery), we will use mixed-effects Poisson regression model including random site effects to account for clustering of patients within sites. We will also model the frequency at which at least 1 specific follow-up test or type of follow-up test is performed using hierarchical logistic regression that includes random site effects. All regression models mentioned above will be fitted with and without potential confounders including age, gender, ethnicity/race, smoking, BMI, nodule size, and any facility-level factors balanced during the randomization. For H3b, to examine whether among all participants with a lung nodule ≤ 15 mm, more intensive surveillance will be associated with a greater number of serious complications related to invasive procedures, similar strategy used for H3a will be adopted. We will model the number of serious procedure-related complications using mixed-effects Poisson regression models and the frequency of patients with any serious complications using hierarchical logistic regression models. For H3c, to investigate whether all participants with a lung nodule ≤ 15 mm, more intensive surveillance will be associated with greater total exposure to diagnostic radiation than less intensive surveillance, we will use mixed effects models and log-transform the radiation exposure to make normal assumption more appropriate.

For H4, binary variables will be generated to indicate adherence to the recommended protocols measured at the level of the ordering provider and the patient. Cross tabulations of the

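### The H3c model for cumulative radiation dose names no covariate and makes no use of the early site dose data the trial already collects. Adjusting for them is a cheap precision gain of unknown size.

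*Combined protocol and SAP*

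**What the plan says.** The Primary endpoints list for Aim 3 includes "Cumulative radiation dose measured by DLP and effective dose". It counts imaging after the baseline CT through 2 years, so the index scan is not part of the outcome.

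In the Analysis Plan, under Aim 3, the H3c model is described only by "we will use mixed effects models and log-transform the radiation exposure to make normal assumption more appropriate". The covariate sentence in that paragraph comes before H3c: "All regression models mentioned above will be fitted with and without potential confounders including age, gender, ethnicity/race, smoking, BMI, nodule size", plus facility factors balanced at randomization. H3b is tied back to the H3a strategy; H3c is not.

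The Cluster Randomization section lists the balancing factors, beginning with "the volume of CT imaging performed, the setting type (integrated healthcare system vs. academic), KPSC vs. other institutions". The rest are race and ethnicity, smoking, inclusion of screening-detected nodules, PET use for 11-15 mm nodules, timing of notification letters and insurance. CT dose is not among them.

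Dose is nevertheless measured early. Under Interventions to be compared: "During the first 3 months of the trial, site project coordinators will review the CT examinations and record radiation dose metrics" (CTDIvol and DLP) "on a large sample of chest CTs performed at their site", at 10-50% of scans, or 100% at California hospitals. Then: "Radiation dose metrics will be calculated monthly by site, provided to the Data Coordinating Center, and reviewed during regular meetings". The use given is quality control of low-dose technique. The Aim 3 Outcomes section adds that CTDIvol and DLP "can thus be extracted for any subjects through review of the images", and that California law requires both in the radiology report.

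**The concern.** Cumulative dose is the sum of dose per scan over scans. Dose per scan depends partly on local technique, and the protocol itself says low-dose technique is often neglected in nodule surveillance. Arm is assigned by hospital or health system, so a site's dose habits belong wholly to one arm. A random site effect models that variation and gives an honest standard error, but it cannot take the variation out of the arm comparison. Only a site-level covariate that predicts later dose can do that.

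At stake are the precision of H3c and its exposure to chance: with at most 24 randomized units, a few high-dose sites falling in one arm could blur or exaggerate the effect of the surveillance protocol on exposure. A measure that might reduce this is already in hand, and no section uses it for analysis.

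**Working it through.** **1. Reproduce the nearest stated figure.** No power is given for H3c. The nearest figure is the Aim 3 procedure count in the sample size section: 32,000 patients, two-sided alpha 0.05, ICC 0.01, 90% power for 0.14 SD. With 24 units:

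- mean cluster size m = 32,000/24 = 1,333
- design effect = 1 + 1,332.3 × 0.01 = 14.32
- effective n per arm = 16,000/14.32 = 1,117
- detectable difference = (1.960 + 1.282) × √(2/1,117) = 0.137 SD

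This rounds to the stated 0.14; power at exactly 0.14 SD is 0.911.

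**2. Where the variance of the contrast lies.** The between-site share is m·ICC/(m·ICC + 1 − ICC) = 13.33/(13.33 + 0.99) = 93%. A patient-level covariate explaining 30% of within-site variance moves the detectable difference only from 0.137 to 0.136 SD. Site-level information is what matters.

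**3. Illustrative effect of a site-level covariate.** The site correlation ρ between early and follow-up dose is not in the documents, so a range is assumed. Treating all contrast variance as between-site, variance falls by the factor 1 − ρ², and power from a 90% start is Φ((1.96 + 1.2816)/√(1 − ρ²) − 1.96):

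- ρ = 0.3: 92.5%; detectable difference 0.14 × √0.91 = 0.134 SD
- ρ = 0.5: 96.3%; 0.14 × √0.75 = 0.121 SD
- ρ = 0.7: 99.5%; 0.14 × √0.51 = 0.100 SD

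The full variance factor, (1 − ICC) + m·ICC·(1 − R²), gives nearly the same: at R² = 0.25, power at 0.14 SD rises from 0.911 to 0.965.

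**4. On the scale of H3c itself.** The protocol expects about 30% less imaging in Group B. If dose is proportional to imaging, the log ratio is ln 0.70 = −0.357. Assume a within-site SD of log dose of 0.8 and SE = √[(4/K)(τ²(1 − R²) + 0.8²/m)], with a t test on K − 2 df (K − 3 adjusted). K is 24, or 14 if only California contributes: 11 Kaiser Permanente Southern California (KPSC) service areas plus three University of California sites, with m = 22,000 × 0.9/14 = 1,414. The between-site SD τ and R² are also assumed.

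| τ | K=24, unadjusted | K=24, R² 0.5 | K=14, unadjusted | K=14, R² 0.5 |
|---|---|---|---|---|
| 0.2 | 0.986 | >0.99 | 0.861 | 0.988 |
| 0.3 | 0.793 | 0.974 | 0.532 | 0.813 |
| 0.4 | 0.550 | 0.836 | 0.335 | 0.573 |

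If dose had the plan's ICC of 0.01, then τ² = 0.64 × 0.01/0.99 = 0.0065 and τ ≈ 0.08. With K = 24 the SE is about 0.034, the ratio 0.357/0.034 is about 10, and unadjusted power is essentially 1.

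**5. Timing.** The review covers the first 3 months of the trial. The earliest surveillance scan in Tables 2, 3 and C1 to C3 is 3 months after the index CT. Early-window data therefore essentially precede protocol surveillance scans. That is an inference from the two schedules; the plan does not state it.

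**The case against.** Leaving out a prognostic covariate does not bias a randomized comparison, and H3c already specifies mixed effects models. That stands: the omission is not an error of validity.

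A reader might infer that H3c would move from 90% to 96% power. The documents do not support this. The benchmark belongs to procedure counts in 32,000 patients and 24 units. For dose, the Aim 3 Outcomes section describes a random sample, of unstated size, from about 22,000 California participants, so H3c may rest on about 14 units. The planned imaging contrast may also make power ample without adjustment (step 4).

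A reader might also infer that scanner technique is the dominant error. The 93% is all between-site variance of a generic outcome at ICC 0.01, and nothing assigns it to technique. Cumulative dose depends on scan count too, and several nodule categories have no recommended scan.

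The covariate is imperfect. It is measured after allocation in an unblinded trial, on chest CTs of any kind, while low-dose quality work is under way. That work may weaken its link with later dose, although Data Management says the initiatives are given equally to all sites. An incidental index CT was ordered for another reason and may not reflect surveillance technique. These points reduce the likely gain without removing the case for adjustment.

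Finally, reading BMI and nodule size as excluded from H3c rests on sentence order. The Abstract promises adjustment for residual imbalances throughout, and step 2 shows such covariates change almost nothing.

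**Conclusion.** The point holds as a cheap improvement. The H3c covariate set is unstated, site dose practice is neither balanced nor adjusted for, and a usable early measure already reaches the Data Coordinating Center. The consequence is lost precision and chance imbalance across 24, or perhaps about 14, randomized units.

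Its size cannot be fixed from the documents. The benchmark illustration runs from a gain of 2.5 points (ρ = 0.3) to 9.5 points (ρ = 0.7). On log dose with 24 units and R² of 0.5, the gain is negligible at a between-site SD of 0.2 and substantial at 0.3 or 0.4, but no section supports any particular value. The quantified gain should not be relied on; the reason to act is the low cost.

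**What to change.** In the Analysis Plan, under Aim 3, state that the H3c model includes a random site effect and is fitted with and without adjustment for:

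- site mean log DLP, restricted to chest CTs from the first 3 months so that it essentially precedes protocol surveillance scans;
- the participant's index-CT log DLP, where available;
- the H3a covariates, for consistency.

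Say which fit carries the conclusion, and state the number of participants and randomized units that will contribute dose data.

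The cost is one or two sentences and one between-site degree of freedom for the site measure (22 to 21 with 24 units). No new site-level data are needed. Index-CT dose will be missing for some participants outside California, so its handling should be stated. If dose has already been compared by arm, the adjusted fit should be reported as supplementary.

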By including a wider spectrum of patients with the target condition, the generalizability of the study findings will be greatly enhanced. Unpublished data from a sample of almost 70,000 members of Kaiser Permanente Southern California (KPSC) with incidentally detected pulmonary nodules indicate that nodules ≤ 10 mm make up 53% of the total population of patients with pulmonary nodules; by increasing the size threshold to ≤ 15 mm, we will include an additional 16% of the total nodule population. Even if as many as one third of the study patients with nodules measuring between 11 mm and 15 mm are not managed initially by CT

surveillance, and instead undergo an initial invasive biopsy or surgical procedure, this would still increase the size of the target population considerably and improve generalizability.

By increasing the size of the target population, we will also improve feasibility, both by casting a wider net that helps us to meet enrollment targets more efficiently, and by increasing the expected prevalence of cancer in the enrolled sample. Based on KPSC data, we estimate that 2% of patients with nodules measuring ≤ 10 mm will have a cancerous nodule, whereas 3% of patients with nodules measuring ≤ 15 mm will have a cancerous nodule (including almost 7% of patients with nodules measuring between 11 mm and 15 mm). Because the study is powered to demonstrate equivalence in stage distribution for patients with cancerous nodules, the increase in the expected frequency of cancer will enable us to meet our goals for sample size much more efficiently. Specifically, we anticipate that approximately 1,056 enrolled patients will have a cancerous nodule, which is greater than our initial estimate of approximately 900 patients. Of note, the original required sample size to achieve statistical power of 90% will not change, and the study will have slightly greater power than originally anticipated to demonstrate equivalence between the two comparison arms.

Finally, the proposed change will not introduce bias and therefore does not threaten validity, because both the more frequent and less frequent surveillance groups will include patients with nodules measuring ≤ 15 mm.

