We will continue recruitment through the end of the study to collect additional data for HTE analyses with greater statistical power for Aim 1. We assume 10% loss to follow-up before final diagnosis is established based on KPSC membership data. This yields an estimated sample size for analyses of 960 individuals with cancerous nodules for Aim 1, and 32,000 individuals with small nodules for Aims 2-4.

Aim 1: For the primary outcome, the baseline risk of progression has not been reported. Conservatively, we assume that 5% of patients will progress from a tumor ≤ 15 mm to a tumor > 20 mm during the surveillance period. Assuming a two-sided alpha of 0.05, and an intraclass correlation coefficient (ICC) of 0.01, a sample size of 888 unique patients with cancerous lung nodules (444 per arm) is required to achieve 83% power to detect an absolute increase in tumor progression of 5 percentage points. Thus, our anticipated sample size of 960 unique patients with cancerous lung nodules provides adequate power to show non-inferiority of the less intensive surveillance strategy for our primary outcome of lung cancer stage $> T1a$ at diagnosis. The most uncertainty in our assumptions is for the ICC. We will have at least 80% power to detect a 5% increase in our primary outcome for ICC values of 0.012 or less. At the baseline ICC value of 0.01, a total sample size of 32,560 enrolled (including 888 patients with cancerous nodules) will have 0.83 power; for an ICC value of 0.012, a total sample size of 35,200 enrolled (960 patients with cancer) will also have 0.83 power.

Aim 2: Prior studies of anxiety and distress in lung cancer screening have shown that the identification of a lung nodule leads to anxiety and emotional distress that subsequently dissipates over 1-2 years.^{56 63 52} For our analyses of anxiety and emotional distress, we will have $> 90\%$ power to detect an effect size of 0.22 standard deviation, assuming an ICC of 0.01, even if the response rate is as low as 5%, resulting in an estimated sample size of approximately 792 respondents in each arm.

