Aim 3: The primary outcome for this aim is the total number of non-invasive and invasive procedures performed from the date of the index CT scan to the end of surveillance. We assume that patients who undergo more intensive surveillance will have 3.5 procedures on average. A sample size of 32,000 individuals with small nodules provides 90% power to detect a difference of 0.14 standard deviations for this outcome, assuming a two-sided alpha of 0.05 and an ICC of 0.01.

We will also compare the frequency of invasive testing among individuals with benign nodules. Based on data from the NLST, we assume that 5% of patients with benign nodules will undergo at least one invasive test. With an estimated sample size of 15,520 individuals with benign nodules in each group, and assuming a 2-sided alpha level of 0.05 and an ICC of 0.01, we will have 90% power to detect a difference between groups in the use of invasive testing of 3.4 percentage points.

Aim 4: For the analysis of radiologist adherence to inclusion of the recommendation for surveillance per protocol in the radiology report, we assume that radiologists will adhere to the assigned protocol for at least 85% of participants in the more intensive group. We estimated the ICC to be 0.19 based on preliminary data on radiologist variability in number of enrolled patients at the KPSC facilities. Assuming a 2-sided alpha of 0.05, we need to review at least 130 reports for enrolled patients at each participating facility to achieve 80% power to detect an improvement in adherence of 5.0 percentage points.

For the analysis of ordering physician adherence with ordering the surveillance test according to the assigned protocol, we assume that 80% of physicians in the more intensive group will be adherent. Assuming a 2-sided alpha of 0.05, our sample size of 16,000 individuals with small nodules in each group will provide >90% power to detect an improvement in adherence of 5.3 percentage points, assuming an ICC of 0.01-0.19.

For the analysis of patient overall adherence with surveillance, we assume that 27% of participants in the more intensive group will be non-adherent, based on the results of our study of guideline-concordant follow-up in veterans with pulmonary nodules.²⁴ Assuming a 2-sided alpha of 0.05, our sample size of 16,000 individuals with small nodules in each group will provide 90% power to detect an improvement in non-adherence of 5.9 percentage points, assuming an ICC of 0.01.

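### The Inclusion Criteria text still claims 90% power for equivalence, while the Aim 1 calculation supports 83% for non-inferiority; the 5-point margin is not named as one and has no decision rule

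*Combined protocol and SAP*

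**What the plan says.** **Inclusion Criteria (Patients and Settings), in the justification of the 15 mm threshold.** The expected gain in cancers is explained with "Because the study is powered to demonstrate equivalence in stage distribution for patients with cancerous nodules". The section cites 1,056 expected cancers against an initial estimate of about 900. It then says that "the original required sample size to achieve statistical power of 90% will not change, and the study will have slightly greater power" than first anticipated, again for equivalence.

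**Sample size and power calculations by aim, Aim 1.** With a two-sided alpha of 0.05, an ICC of 0.01 and an assumed 5% progression risk, "888 unique patients with cancerous lung nodules (444 per arm) is required to achieve 83% power to detect an absolute increase in tumor progression"; the increase meant is 5 points. The 960 cancers expected are said to be a number that "provides adequate power to show non-inferiority of the less intensive surveillance strategy". A second statement gives 0.83 power for 960 cancers at an ICC of 0.012. Hypothesis H1a is also one of non-inferiority.

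**Loss to follow-up, same section.** From 35,200 enrolled, 3.0% cancers (1,056) and 10% loss: "This yields an estimated sample size for analyses of 960 individuals with cancerous nodules for Aim 1", and 32,000 nodules for Aims 2-4. Related figures are "a total sample size of 32,560 enrolled (including 888 patients with cancerous nodules) will have 0.83 power" and, for Aim 2 at a 5% response rate, "resulting in an estimated sample size of approximately 792 respondents in each arm". Aim 3 continues with "A sample size of 32,000 individuals with small nodules provides 90% power to detect a difference of 0.14 standard deviations".

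**Analysis Plan, H1a primary endpoint.** Hierarchical logistic regression with random site effects, fitted with and without covariates. It states no margin, confidence limit or conversion to a risk difference.

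**The concern.** Non-inferiority of less intensive surveillance on tumour stage is the trial's main conclusion, so its power, claim and decision rule should read the same throughout.

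They do not. A reader of the Inclusion Criteria section takes the chance of missing true non-inferiority to be 1 in 10 or less. The Aim 1 inputs, with the loss computed as stated, imply about 1 in 7 (ICC 0.01) to 1 in 6 (ICC 0.012). Equivalence is also a different, two-sided claim that needs a larger sample for the same power.

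The Aim 1 paragraph calls the 5 points an increase to be detected, which is superiority language. The planned logistic model yields an odds ratio, and a 5-point difference corresponds to different odds ratios at different reference risks. The plan says the baseline risk has not been reported. Without a stated step, the same data could pass or fail according to a choice made after fitting.

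**Working it through.** **Inputs.** Risk 5% in both arms, limit 0.05, two-sided alpha 0.05 (one-sided 0.025, z = 1.96), ICC 0.01 or 0.012 (Aim 1 paragraph); 24 sites (opening of the sample size section). Equal cluster sizes and a normal approximation are my assumptions.

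**Formulas.** For N cancers in total: design effect D = 1 + (N/24 − 1) × ICC; effective n per arm = (N/2)/D; power = Φ(0.05/√(2 × 0.05 × 0.95/n) − z).

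**1. Reproducing the plan's 83%.** N = 888, ICC 0.01: D = 1 + 36 × 0.01 = 1.36; n = 444/1.36 = 326.5; standard error 0.01706; 0.05/0.01706 = 2.931; Φ(2.931 − 1.96) = 83.4%. N = 960, ICC 0.012: D = 1.468, n = 327.0, power 83.5%. Both printed figures stand. Read instead as superiority (5% against 10%), 888 cancers give about 68%. Only the non-inferiority reading fits.

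**2. Looking for the 90%.**

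| Cancers | Power, ICC 0.01 | Power, ICC 0.012 |
|---|---|---|
| 888 | 83.4% | 81.5% |
| 900 | 83.8% | |
| 950 | 85.2% | 83.2% |
| 960 | 85.4% | 83.5% |
| 1,056 (no loss) | 87.6% | 85.7% |

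At ICC 0.01, 90% needs about 1,185 analysable cancers, or 1,185/(0.9 × 0.03) ≈ 43,900 enrolled. Alternatively, the ICC would have to be about 0.0052 or less at 960 cancers, or 0.0075 or less at 1,056.

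**3. Equivalence.** With two one-sided tests at 0.025 within ±5 points and no true difference, power is 2 × (non-inferiority power) − 1: about 67% at 888 and 71% at 960 (ICC 0.01).

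**4. Margin against model.** The odds ratio matching a 5-point increase depends on the reference risk. At 5% it is (0.10/0.90)/(0.05/0.95) = 2.11; at 3% it is 2.81; at 10% it is 1.59. The 3% and 10% are illustrations by assumption.

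**5. Loss.** 1,056 × 0.9 = 950 and 35,200 × 0.9 = 31,680. The printed values are 1,056/1.1 = 960 and 35,200/1.1 = 32,000, an effective loss of 9.1%. Likewise 32,560 × 0.03/1.1 = 888, whereas 32,560 × 0.03 × 0.9 = 879; 888 cancers need 888/(0.9 × 0.03) ≈ 32,889 enrolled. Aim 2's 792 equals 31,680 × 0.05/2 (32,000 would give 800), so the section uses both conventions. Downstream, 16,000 per group becomes 15,840, and 15,520 benign (16,000 × 0.97) becomes 15,840 × 0.97 ≈ 15,365.

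Effect on Aims 3 and 4 (12 sites per arm, ICC 0.01, 90% power): 0.137 SD with either 16,000 or 15,840 (printed 0.14); 3.43 points with either 15,520 or 15,365 (printed 3.4); 5.85 points for patient adherence with either 16,000 or 15,840 (printed 5.9). Effective size hardly moves because clusters are large: 16,000/14.32 ≈ 1,117 against 15,840/14.19 ≈ 1,116.

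**The case against.** The Inclusion Criteria text explains a past design change and ties the 90% to the original requirement, so it can be read as history. H1a and the Aim 1 paragraph both say non-inferiority, and nobody would choose the test from the eligibility section. This stands in part: the planned test is not in doubt. But the text is current, uses the present tense for equivalence, says the 90% requirement is unchanged and cites today's 1,056 cancers. A reader will take 90% as applying now.

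More cancers may accrue. The sample size section calls 35,200 a minimum and says recruitment continues to the end of the study; its target population of 45,000 would give 45,000 × 0.03 × 0.9 = 1,215 cancers and 90.5% power at ICC 0.01 (88.6% at 0.012). But the Subgroup Analyses section says the enrolment period was limited so that everyone has two years of follow-up. The two statements conflict, and neither commits to a number that reaches 90%.

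The loss slip is nearly immaterial, since the Missing Data section expects at most 10% and 9.1% lies within that. I agree on its size. It remains inconsistent with the stated 10% and with Aim 2.

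Quoting 85% instead could replace one unsupported figure with another. This stands. At 950 cancers a t reference with 22 degrees of freedom gives 81.9% (ICC 0.01) or 79.8% (ICC 0.012). An assumed cluster-size coefficient of variation of 0.6, a figure the documents do not give, yields 81.6% or 79.0%.

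**Conclusion.** The 90% and the equivalence wording are wrong as current statements. On the Aim 1 inputs, non-inferiority power is 83.4% at 888 cancers, 85.4% at 960 and 87.6% at 1,056 (ICC 0.01, 24 equal sites, equal true risks, normal approximation). The 5 points act as an absolute margin but are not named as one, and H1a has no rule linking the logistic model to them. The loss slip is a minor correction.

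Three stronger readings are not supported:

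- **That the 83% is miscalculated.** It reproduces in both places where it is printed.
- **That the 90% came from a one-sided alpha of 0.05.** That does give 90.1% at 888, but the documents do not say so, and the Aim 1 paragraph uses a two-sided 0.05.
- **That the loss slip weakens the trial.** It costs 0.3 points of primary power or less and alters none of the printed Aim 3 and 4 differences checked.

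This should be fixed. It does not require a redesign.

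**What to change.** 1. **Inclusion Criteria:** replace equivalence by non-inferiority, and replace the 90% claim by a reference to the Aim 1 power (83% at 888 cancers and ICC 0.01, or at about 950-960 cancers and ICC 0.012). If about 85% at 950 cancers and ICC 0.01 is quoted, state the equal-cluster and normal-approximation assumptions beside it.
2. **Aim 1 power paragraph:** name the 5 percentage points as the absolute non-inferiority margin.
3. **H1a analysis:** name one model, with or without covariates, as decisive. Convert its result to a risk difference by a stated method, and compare the upper limit of the two-sided 95% confidence interval with 5 points. A one-sided 95% limit would correspond to alpha 0.05, so the wording must be exact.
4. **Recruitment:** reconcile the statement that recruitment continues through the end of the study with the limited enrolment period.
5. **Minor figures:** 950 for 960, 31,680 for 32,000, 15,840 for 16,000 per group, about 15,365 for 15,520, and about 32,889 for 32,560. The printed Aim 3 and 4 detectable differences can stay.

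The cost is wording, a few figures and one reporting step after model fitting, with no added patients. The 90% claim is lost. The Aim 1 Outcomes section scheduled linkage, cleaning and analysis to finish by January 31, 2023. If outcomes have already been analysed, the rule in item 3 must be labelled post hoc, which weakens it.
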